# 1 OVERVIEW AND INVESTIGATIONAL PLAN

## 1.1 STUDY DESIGN AND RANDOMIZATION

This is a Phase 3, multicenter, 56-week, randomized, open-label for the drug (efpeglenatide and dulaglutide) and double-blind for the doses of efpeglenatide, active-controlled, 3-arm, parallel group study in participants with type 2 diabetes mellitus (T2DM) inadequately controlled with metformin.

After a Screening phase of up to 3 weeks, participants will be centrally randomized (using permuted block randomization schedule) via Interactive Response Technology (IRT) in a 1:1:1 ratio to 1 of the following 3 treatment groups:

- efpeglenatide 4 mg
- efpeglenatide 6 mg
- dulaglutide 1.5 mg

Randomization will be stratified by Screening hemoglobin A1c (HbA1c) ( $<8.0\%$ ,  $\geq 8.0\%$ ) and Visit 3 (Baseline, Day 1) body mass index (BMI) ( $<30 \text{ kg/m}^2$  and  $\geq 30 \text{ kg/m}^2$ ). Participants will receive open-label, active-controlled treatment for 56 weeks. Additional details on the study design and plan are provided in [Section 1.4](#).

Approximately 900 participants (300 participants per treatment group [details in [Section 1.3](#)] will be randomized.

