### 1.3 DETERMINATION OF SAMPLE SIZE

The sample size calculations are performed based on the primary endpoint, change in HbA1c (%) from Baseline to Week 56.

Assuming a common standard deviation of 1.1%, and the true difference between efpeglenatide and dulaglutide is zero, 300 participants per arm will ensure that the upper bound (UB) of the 2-sided 95% CI of the adjusted mean difference would not exceed 0.3% with 91% power.

Hence, there are 3 parallel dosing arms as follows:

- Efpeglenatide 4 mg, N=300
- Efpeglenatide 6 mg, N=300
- Dulaglutide 1.5 mg, N=300

[figure not shown]

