#### **2.4.4.1 Analysis of primary efficacy endpoint**

##### **Hypothesis Testing of the Primary Endpoint:**

For the primary efficacy variable of change from Baseline to Week 56 in HbA1c, the following statistical null hypothesis and alternative will be tested as:

- H0: efpeglenatide - dulaglutide  $\geq$  0.3%
- H1: efpeglenatide - dulaglutide  $<$  0.3%

The null hypothesis will be tested at a 1-sided alpha level of 0.025 using a non-inferiority margin of 0.3%.

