***Retrieved-dropout multiple imputation method:***

The retrieved-dropout multiple imputation sensitivity analysis will have 2 separate parts as follows:

1. Missing endpoint data in participants who prematurely discontinue the study treatment before the Week-56 visit will be imputed using a model built separately in each arm and estimated from participants in the same treatment arm who prematurely discontinue the study treatment before the Week-56 visit but have the measurement for the endpoint (retrieved dropouts). Considering that the number of participants in each treatment arm who discontinue the study treatment but have the measurement for the endpoint is expected to be small, a simple imputation model will be used, where only the Hb1Ac baseline measurements are included as the predictor. Each treatment group will have their own imputation model.
2. Missing endpoint data in all participants who stay on the study treatment until the Week-56 visit will be imputed using a model built separately in each arm and estimated from participants in the same treatment arm who stay on the study treatment until Week-56 visit and have the endpoint measurement, where randomization strata and Hb1Ac baseline measurements are included as the predictors.

In both parts, the missing data will be imputed using the regression method. After imputation, the completed data sets will be analyzed using an ANCOVA model similar to the primary analysis.

If there are no sufficient data to support the imputation approach in item 1 described above (less than 5 participants in any arms who prematurely discontinue the study treatment before the endpoint visit but have the measurement for the endpoint), a back-up method will be used. In particular, missing endpoint data in all participants, regardless of staying on the study treatment or not, will be imputed using a model built separately in each arm and estimated from participants in the same treatment arm with endpoint data, where randomization strata and corresponding baseline values are included as the predictors.

SAS pseudo-codes are provided in [Appendix A](#).

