***2.4.4.1.1 Sensitivity analysis due to COVID-19 at Week 56 (HbA1c)***

Sensitivity analysis will be performed using ANCOVA (as specified in [Section 2.4.4.1](#)) with missing values imputed based upon BOCF-like MI method and MAR approach as described below, if there are more than 10 participants in total (regardless of treatment group) with missing endpoint data due to COVID-19. Participants with missing endpoint data due to COVID-19 are identified in [Appendix C](#).

- For participants with missing HbA1c values at Week 56 not due to Covid-19, the missing values will be imputed using a random draw from a normal distribution with mean equal to their Baseline HbA1c and the standard deviation equal to the pooled standard deviation calculated from the square root of the mean square error estimated from a regression model with Baseline HbA1c as the dependent variable and randomization strata and treatment as the covariates.
- For participants with missing HbA1c values at Week 56 due to Covid-19 in each group, the missing values will be imputed using separate models including the data at all scheduled visits within the same treatment group assuming missing at random.
  - Step 1: Use the Markov Chain Monte Carlo method in conjunction with the IMPUTE=MONOTONE option in PROC MI to create an imputed data set with a monotone missing pattern
  - Step 2: Based on the MONOTONE data sets obtained from Step 1, build the imputation model using the regression method sequentially for each scheduled visit. The imputation model will include the randomization stratum of HbA1c value at Screening (<8.0, ≥8.0%), Visit 3 (Day 1) BMI (<30, ≥30 kg/m^2), corresponding baseline values and preceding scheduled postbaseline values.

Participants without data at the endpoint visit will be summarized by treatment status (discontinued, completed) and by impact of COVID-19 on participant (yes, no) for each treatment group.

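### The on-treatment and back-up models of the retrieved-dropout imputation leave out HbA1c at Weeks 12, 30 and 43, which the SAP's COVID-19 imputation uses

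*SAP*

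**What the plan says.** The retrieved-dropout method in SAP 2.4.4.1 has three imputation models, each fitted separately by arm.

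- **Item 1** (stopped treatment before Week 56): baseline HbA1c only. The stated reason is that few such participants are expected to have an endpoint value.
- **Item 2** (on treatment to Week 56): "where randomization strata and Hb1Ac baseline measurements are included as the predictors". No reason is given for stopping there.
- **Back-up** (replaces both if any arm has fewer than 5 retrieved dropouts): applies to every missing endpoint, on or off treatment, "where randomization strata and corresponding baseline values are included as the predictors".

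The Appendix A code agrees with the text. The PROC MI statements for item 2 and the back-up list the two strata, baseline and Week 56, with no post-baseline visit.

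SAP Appendix D schedules HbA1c at Weeks 12, 30 and 43. The COVID-19 sensitivity analysis in SAP 2.4.4.1.1 imputes the same endpoint by arm under missing at random, using strata together with "corresponding baseline values and preceding scheduled postbaseline values". Its code names all three visits.

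**The concern.** Under item 2 or the back-up, two participants in the same arm with equal baseline and strata get the same imputation distribution, whatever their Week 43 HbA1c. Yet Week 43 should be informative. Protocol 3.1 says HbA1c reflects the previous 120 days. Week 43 (Day 301) and Week 56 (Day 392) are 91 days apart, so the two windows overlap by 120 − 91 = 29 days.

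Missing at random given baseline alone is a stronger assumption than missing at random given the HbA1c course. If it fails differently in the two arms, the comparison is biased.

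This analysis also has a distinct role. The tipping-point analysis keeps the imputation method of the primary analysis, the COVID-19 analysis keeps it for missingness not due to COVID-19, and the completers analysis uses observed values only. The retrieved-dropout analysis is the one planned check that replaces the baseline-like assumption for all missing endpoints.

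**Working it through.** **Plan's own figure.** Hypothesis: "tested at a 1-sided alpha level of 0.025 using a non-inferiority margin of 0.3"% (SAP 2.4.4.1). SAP 1.3: "Assuming a common standard deviation of 1.1%, and the true difference between efpeglenatide and dulaglutide is zero", 300 per arm, upper bound that "would not exceed 0.3% with 91% power". Randomization is 1:1:1 (SAP 1.1).

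- SE = 1.1 × √(2/300) = 0.0898
- Power = Φ(0.3/0.0898 − 1.96) = Φ(1.38) = 0.916; 0.915 with the noncentral t on 598 df

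The stated 91% is reproduced. Nothing below changes the sample size or power.

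**Is there room for the extra predictors?** Two strata, baseline and three visits make six predictors. If a fifth of a planned arm could not serve as donors (assumption), 300 × 0.8 = 240 donors remain. The small-number reason for item 1 does not carry over.

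**Error for one participant.** Let ρ be the correlation between Week 43 and Week 56 after adjusting for baseline. The documents do not give it, so take 0.5, 0.7 and 0.85, with the planning SD of 1.1 as residual SD. For someone k SD above the arm's expectation at Week 43, expected Week 56 HbA1c exceeds the baseline-only prediction by ρ × k × 1.1. For k = 1 that is 0.55, 0.77 and 0.94 points. A participant below expectation is imputed too high by the same amount.

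**Precision.** Adding Week 43 cuts the residual SD from 1.1 to 1.1 × √(1 − ρ²) = 0.95, 0.79 and 0.58.

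**Effect on the arm comparison.** Simulation: 300 per arm, 200 trials per setting, baseline mean 8.2 and SD 0.8, mean change −1.3, strata omitted. Missingness follows a logistic model in the Week 43 residual, log-odds slope 1 per SD, the same in both arms. All of these are assumptions except the 300 and the 1.1. Percentages missing are efpeglenatide versus dulaglutide; negative bias favours efpeglenatide.

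| ρ | Mean error in the missing, baseline only | Bias, 15% vs 5% | Bias, 20% vs 10% | Bias, equal missingness (10% or 5% in both arms) |
|---|---|---|---|---|
| 0.5 | −0.47 to −0.52 | −0.049 | −0.041 | within 0.001 |
| 0.7 | −0.68 to −0.71 | −0.064 | −0.066 | within 0.001 |
| 0.85 | −0.80 to −0.87 | −0.085 | −0.077 | within 0.002 |

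Check by hand at ρ = 0.7, 15% vs 5%: 0.15 × 0.689 − 0.05 × 0.713 = 0.068, against 0.064 simulated. As a share of the margin, the range is 0.041/0.3 = 14% to 0.085/0.3 = 28%. Swapping the missingness rates between arms reverses the sign.

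With Week 43 in the model, the mean error in the missing is within 0.03 and the between-arm bias within 0.004. This follows from the set-up, because the simulation makes missingness depend on Week 43 and then conditions on it. With slope 0 (missingness unrelated to interim HbA1c), both models have between-arm bias within 0.004.

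**Item 2 alone.** SAP 2.5.4 fills a missing Week 56 HbA1c from an unscheduled, end-of-treatment or end-of-study value within 30 days of Day 392. Few on-treatment participants should remain without a value. If the arms differ by 1 to 2 percentage points (assumption), the bias is 0.01 × 0.47 = 0.005 to 0.02 × 0.87 = 0.017 points, about 2% to 6% of the margin.

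**The case against.** The case against giving this much weight is strong in several respects.

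- **Who is affected.** Someone with a poor Week 43 value who then stops treatment falls under item 1, not item 2. The back-up reaches that person only if its trigger is met. This stands.
- **Mechanism.** SAP 2.4.4 regards COVID-19 missingness as likely at random, and SAP 2.3.1.2 records early termination by the sponsor. Neither cause need track interim HbA1c. After Week 30, HbA1c of 8.0% or more meets a rescue criterion (protocol Table 3), and post-rescue values count. Rescue could weaken the link between Week 43 and Week 56. Both stand as reasons to doubt the larger values of ρ and a strong dependence.
- **The remedy in the back-up.** There, participants who stopped are imputed from everyone in the arm with endpoint data. Someone who responded well and stopped for intolerance would carry good on-treatment interim values into the imputation, giving a result more optimistic than the arm average. This stands, and it makes the remedy less clear-cut in the back-up than in item 2.
- **Reliance.** The primary analysis draws around each participant's own baseline, and the tipping-point analysis penalises missing efpeglenatide values until noninferiority fails. Neither uses these models. This stands.

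None of it explains why two missing-at-random imputations of one endpoint in one SAP use different information.

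A reader might also infer that the whole shift in one arm is the between-arm bias. With 10% missing that shift is 0.05 to 0.08 points in the simulation. Reading it as the bias requires 10% Week-43-driven loss in one arm and none in the other, and nothing in the documents supports that case.

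**Conclusion.** The omission is real, in both text and code, and no reason is given for it. Its sure cost is precision in one sensitivity analysis. Bias in the arm comparison needs missingness that depends on interim HbA1c and differs by arm. Under the assumptions shown, a 10-point difference in missingness gives about 0.04 to 0.09 points. Equal missingness with the same mechanism in both arms gives about zero, and item 2 alone probably gives very little.

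A reader might conclude that the plan tilts the trial towards noninferiority by scoring failing participants as average responders. The documents do not support that. The bias favours whichever arm loses more poor responders, so it may be conservative. The average in question is the arm's own, given baseline and strata. The primary and tipping-point analyses do not change. Priority: consider.

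**What to change.** - **Item 2:** adopt the two-step specification of SAP 2.4.4.1.1. Use MCMC to reach a monotone pattern, then sequential regression by arm on strata, baseline and Weeks 12, 30 and 43. Change the PROC MI VAR and MONOTONE statements in Appendix A to match.
- **Item 1:** leave it simple, for the reason the SAP gives.
- **Back-up:** add the same visits, and state the downside that on-treatment interim values of participants who later stop may carry an on-treatment response into their imputed Week 56 value.
- If the interim visits are to stay out, say why.

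The cost is SAP wording and adapting existing pseudo-code, with no new data. The COVID-19 code cannot be copied unchanged. Its ANCOVA step reads a dataset other than the combined one it has just built, and it derives change from baseline only for the values imputed as not due to COVID-19.

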***Analysis on completers:***

For participants in ITT population who completed the 56-week treatment period and did not start any rescue therapy before the end of the period, the primary endpoint will be assessed too by the same ANCOVA model as used for the primary analysis using the observed values.

***2.4.4.1.1 Sensitivity analysis due to COVID-19 at Week 56 (HbA1c)***

Sensitivity analysis will be performed using ANCOVA (as specified in [Section 2.4.4.1](#)) with missing values imputed based upon BOCF-like MI method and MAR approach as described below, if there are more than 10 participants in total (regardless of treatment group) with missing endpoint data due to COVID-19. Participants with missing endpoint data due to COVID-19 are identified in [Appendix C](#).

- For participants with missing HbA1c values at Week 56 not due to Covid-19, the missing values will be imputed using a random draw from a normal distribution with mean equal to their Baseline HbA1c and the standard deviation equal to the pooled standard deviation calculated from the square root of the mean square error estimated from a regression model with Baseline HbA1c as the dependent variable and randomization strata and treatment as the covariates.
- For participants with missing HbA1c values at Week 56 due to Covid-19 in each group, the missing values will be imputed using separate models including the data at all scheduled visits within the same treatment group assuming missing at random.
  - Step 1: Use the Markov Chain Monte Carlo method in conjunction with the IMPUTE=MONOTONE option in PROC MI to create an imputed data set with a monotone missing pattern
  - Step 2: Based on the MONOTONE data sets obtained from Step 1, build the imputation model using the regression method sequentially for each scheduled visit. The imputation model will include the randomization stratum of HbA1c value at Screening (<8.0, ≥8.0%), Visit 3 (Day 1) BMI (<30, ≥30 kg/m^2), corresponding baseline values and preceding scheduled postbaseline values.

Participants without data at the endpoint visit will be summarized by treatment status (discontinued, completed) and by impact of COVID-19 on participant (yes, no) for each treatment group.

***Assessment of missing data:***

The availability of data (yes, no) at the endpoint visit (Week 56) will be summarized by treatment status (discontinued, completed) by treatment group.

Patients without data at the endpoint visit be summarized by treatment status (discontinued, completed) and by impact of Covid-19 on participants (yes, no) for each treatment group. Reasons for missing primary efficacy endpoint (ie, HbA1c at Week 56) will be listed.

**Assessment of treatment effect by subgroup:**

Primary efficacy endpoint will be further analyzed to examine the consistency of the treatment effect across the subgroups defined by the following Screening or Baseline covariates:

- Race (White, Black or African American, Asian, Other) (any race groups with fewer than 5 participants may be combined with “Other” category as appropriate)  
Note: For all efficacy and safety subgroup analyses, race groups “Not reported”, “Unknown”, and participants who report more than one race will be considered “Other”.
- Ethnicity (Hispanic or Latino, Not Hispanic or Latino)
- Age group (<50, ≥50 to <65, ≥65)
- Gender (Male, Female)

- Duration of diabetes (<10, ≥10 years)
- Baseline HbA1c (<8.0, ≥8.0%)
- Baseline BMI (<30, ≥30 to <40, ≥40 kg/m^2)
- Region (North America, Eastern Europe (including Hungary and Poland))
- Baseline estimated GFR categories (mL/min/1.73m^2): (<60; ≥60 to <90, ≥90)

The treatment effects (efpeglenatide 4, or 6 mg, versus dulaglutide 1.5 mg) across the subgroups defined for each of these factors will be estimated for the change from Baseline to Week 56 in HbA1c in the ITT population, and using a similar imputation approach (ie, BOCF-like MI method under MNAR framework) as applied to the analysis of the primary efficacy endpoint. The ANCOVA model will include treatment groups (efpeglenatide 4, or 6 mg, dulaglutide 1.5 mg) and randomization stratum of Screening HbA1c (<8.0, ≥8.0%), randomization stratum of Visit 3 (Baseline, Day 1) BMI (<30, ≥30 kg/m^2), subgroup factor, treatment-by-subgroup factor, and region as fixed factors and using Baseline HbA1c value as a covariate. The adjusted estimates of treatment mean differences (each efpeglenatide dose versus dulaglutide) with SE and 95% CIs will be provided as appropriate across the subgroups. A graphical presentation of the results (ie, forest plot) will also be provided.

In the case that the subgroup factor (eg, Baseline HbA1c, Baseline BMI) is identical or similar to a randomization strata factor, only the subgroup factor (as a single factor or an interaction term) will be included in the model in order to avoid the issue of collinearity in the analysis. The corresponding strata factor will not be included in the model. In case that the subgroup factor is country, the region will not be included in the model.

Descriptive statistics for change from baseline in HbA1c to Week 30 will be presented by ADA status the efpeglenatide groups:

- ADA status (positive, negative) at Baseline, if ≥ 5% of patients are ADA positive;

Treatment-emergent ADA status (positive, negative).

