**Table 7 - Other analyses**

Endpoint	Statistical Analysis Methods
Efpeglenatide ADA	
Summaries of ADA data will be for participants treated with efpeglenatide only. All summaries related to kinetics of ADA response (ADA status and magnitude, ADA attributes, participant status, ADA incidence) will be descriptive; no statistical significance tests will be performed on ADA data:
 
 
• Number and percentage of participants by ADA status (positive/negative) at scheduled visits
 
• Number and percentage of participants with treatment-induced ADAs (among the participants ADA negative at baseline) during the study period
 
• Number and percentage of participants with treatment-boosted ADAs (among the participants ADA positive at baseline) during the study period
 
• ADA titer at scheduled time point will be summarized by visit using descriptive statistics by number (n), median, quartiles, minimum, and maximum
 
• Number and percentage of participants by ADA cross-reactivity to endogenous GLP-1 (positive or negative) at scheduled visits
 
• Number and percentage of participants by ADA cross-reactivity to endogenous glucagon (positive or negative) at scheduled visits
 
• Number and percentage of participants with ADAs directed against the PEG linker of efpeglenatide at scheduled visits
 
 
Correlation, scatterplots and/or subgroup analyses will be conducted as appropriate to assess the relationship between immunogenicity endpoints and efficacy/safety assessments.

PK endpoints: serum concentration of efpeglenatide at predose and post dose	
Efpeglenatide predose and postdose serum concentrations of participants in the efpeglenatide groups will be listed and summarized in the PK population, using descriptive statistics by n, geometric mean, coefficient of variation, median, minimum and maximum.

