### **2.4.5.7 Analyses of other safety endpoints**

#### **Anti-drug Antibody:**

An anti-drug antibody positive participant is defined as a participant with at least one treatment-induced or treatment-boosted ADA-positive sample at any time.

Summaries of ADA data will be provided for participants treated with efpeglenatide only. All summaries related to kinetics of ADA response (ADA status and magnitude, ADA attributes, participant status, ADA incidence) will be descriptive; no statistical significance tests will be performed on ADA data. The incidence of ADA status (positive/negative) will be summarized by visit, treatment, and individual titer for the ADA population. Incidence of treatment induced and treatment-boosted (treatment emergent) ADA during on-study period will be summarized by treatment. Incidence of participants with ADA cross-reactivity to endogenous GLP-1 (positive/negative), and to endogenous glucagon (positive/negative) will be summarized by visit and treatment. Incidence of participants with ADA directed against PEG linker, HMC001 moiety and exendin-4 moiety (positive/negative) will be summarized by visit and treatment.

Incidence of participants with neutralizing antibodies against efpeglenatide and against endogenous GLP-1 and Glucagon will be summarized by visit and treatment.

ADA data from unscheduled visits (due to SAE for example) will not be included in summary and will be presented only in ADA values listing.

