| Week                             | -3                           | -1         | 0
base-
line             | 2          | 4          | 8          | 12         | 18          | 24          | 30          | 36          | 43          | 50          | 56 a | Last
IMP+6
weeks                 |  |
| Acceptable range (days)          | -21
to -11                | -7
(±3) | 1                              | 14
(±3) | 28
(±3) | 56
(±3) | 84
(±3) | 126
(±3) | 168
(±3) | 210
(±3) | 252
(±5) | 301
(±5) | 350
(±5) | 392
(±5)     | 434
(±7)                            | V2 can be done as soon as the screening eligibility is confirmed
V3 can be done 4 to 10 days after V2
V3 should be done at least 11 days after V1 (to allow IMP to be sent to the site) and no later than 21 days after V1   |
| Antidrug antibody (ADA) sampling |                              |            | X                              |            | X          |            | X          |             |             | X           |             |             |             | X               | X                                      | Participants positive for ADA at EOS, and who experienced severe injection site or hypersensitivity reaction at any time during the study, will be asked to provide sample for anti-efpeglenatide antibodies assessments 4 and 6 months after the end of the treatment. Blood samples are to be collected to assess the efpeglenatide ADA status (positive or negative) and level (titer) applicable for the participants assigned to efpeglenatide. |

| Procedure                       | Screening
(up to 3 weeks) |            | Treatment Period
(56 Weeks) |            |            |            |            |             |             |             |             |             |             |                 | Post treatment
Follow-up
(6 wks) | Notes  |
|---------------------------------|------------------------------|------------|--------------------------------|------------|------------|------------|------------|-------------|-------------|-------------|-------------|-------------|-------------|-----------------|--|--|
|                                 | 1                            | 2          | 3                              | 4          | 5          | 6          | 7          | 8           | 9           | 10          | 11          | 12          | 13          | 14              | 15                                     |  |

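### Week 30 HbA1c is split by a treatment-emergent ADA status that also counts antibodies first detected at Week 56 or end of study

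*SAP*

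**What the plan says.** SAP 2.4.4.1, under the assessment of treatment effect by subgroup, lists the subgroup factors and analyses all of them on the HbA1c change to Week 56. The ADA paragraph that follows changes the time point: "Descriptive statistics for change from baseline in HbA1c to Week 30 will be presented by ADA status the efpeglenatide groups". It names two splits. The first is "ADA status (positive, negative) at Baseline, if ≥ 5% of patients are ADA positive". The second is treatment-emergent status, positive or negative, with no date limit.

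The rule for the second split has to be taken from SAP 2.4.5.7: "An anti-drug antibody positive participant is defined as a participant with at least one treatment-induced or treatment-boosted ADA-positive sample at any time". The same section adds: "Incidence of treatment induced and treatment-boosted (treatment emergent) ADA during on-study period will be summarized by treatment". SAP 2.1.4 runs the on-study period from first injection to the final scheduled visit, or to the last available information in those who leave early, whichever is later. SAP 2.1.5.1 defines boosting as at least a doubling of the baseline titer.

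The schedule of activities (Protocol 1.3; SAP Appendix D) places ADA draws at Day 1, Weeks 4, 12, 30 and 56, and EOS. Protocol Table 7 (Section 9.4.3) plans correlations, scatterplots or subgroup analyses, where appropriate, to "assess the relationship between immunogenicity endpoints and efficacy/safety assessments", but fixes neither a time point nor a window for status.

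**The concern.** The treatment-emergent split groups an outcome by information that can arise after the outcome was measured. Someone whose samples are negative through Week 30 and who first tests positive at Week 56 or EOS joins the positive group, carrying an HbA1c value taken before any antibody was detected. If such participants look like ADA-negatives at Week 30, they pull the two groups together and weaken any antibody signal.

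The classifier also depends on how long a participant was observed. SAP 2.3.1.2 records that the sponsor terminated the study early, so some participants had less time after Week 30 in which a first positive could be found. Protocol 7.1.1 drops ADA assessment from the remaining visits of participants who stop treatment, attend an early end-of-treatment visit and stay in the study. The split therefore reflects retention as well as antibody formation.

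The time point matters too. Protocol 3.1 justifies 56 weeks of treatment by the need to show that the effect lasts at least 12 months. No table specified in the SAP gives Week 56 HbA1c by ADA status, so a waning of effect linked to antibodies after Week 30 would not appear in any planned table.

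**Working it through.** The plan states no figure for this analysis, so there is none to reproduce. The check is of timing, followed by an illustration of size.

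**Timing**
- SAP 2.5.4 targets Week 30 at Day 210 and Week 56 at Day 392. The schedule puts EOS at Day 434 for a participant who completes treatment.
- Week 56 minus Week 30: 392 − 210 = 182 days; 182/7 = 26 weeks.
- EOS minus Week 30: 434 − 210 = 224 days; 224/7 = 32 weeks.
- Post-baseline draws: Weeks 4, 12, 30, 56 and EOS, five in all. Three fall on or before the Week 30 visit and two after it.
- Nothing in either document confines status for this table to the first three.

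**Which split is affected**
- Baseline ADA status is fixed before treatment, so later samples cannot alter it.
- Treatment-emergent status is affected, and only through samples that are treatment-induced or treatment-boosted. An unboosted pre-existing positive does not count.

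**Size, on assumptions**
Let m₊ be the mean Week 30 change in participants detected positive by Week 30, m₋ the mean in those never positive, d = m₊ − m₋, and f the share of the positive group first detected after Week 30. Assume those late converters also have mean m₋ at Week 30. Then:
- positive-group mean = (1 − f)·m₊ + f·m₋
- displayed difference = (1 − f)·m₊ + f·m₋ − m₋ = (1 − f)·d

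| f | shown if d = 0.3% | shown if d = 0.5% |
|---|---|---|
| 5% | 0.285 | 0.475 |
| 10% | 0.27 | 0.45 |
| 20% | 0.24 | 0.40 |
| 30% | 0.21 | 0.35 |
| 40% | 0.18 | 0.30 |

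To relate f to conversion rates, suppose 25% of participants are positive by Week 30 and a further 5, 10 or 15% turn positive only later. Then f = 0.05/0.30 = 17%, 0.10/0.35 = 29% or 0.15/0.40 = 38%. With d = 0.40%, the table would show 0.40 × 0.25/0.30 = 0.33, 0.40 × 0.25/0.35 = 0.29, or 0.40 × 0.25/0.40 = 0.25. The values of 25%, 5 to 15%, f and d are all assumed; none comes from the documents.

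**The case against.** The strongest reply is that Week 30 may be a drafting slip. The SAP's table of changes (Section 1.6) describes this same summary as HbA1c at Week 56. If that was the intention, the Week 56 draw coincides with the outcome, and only first positives at EOS, 434 − 392 = 42 days later, would follow it. A change log does not override the current text, and the difference between the two is not itself an error. It is a good reason to confirm the intended time point.

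Second, SAP 2.1.5.1 defines an indeterminate response that covers a participant positive only at the last sample, or at the last two samples less than 16 weeks apart. That captures many late converters, but the HbA1c table does not use the category.

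Third, a reader might infer that an antibody effect at Week 56 cannot be examined at all. The documents do not support that. Protocol Table 7 leaves room for further analyses, and ADA status and HbA1c are each summarised by visit. What can be said is that no Week 56 table by ADA status is specified.

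Fourth, a reader might infer that late converters had no antibodies when HbA1c was measured. The draws show only that none had been detected. Onset could fall anywhere in the 26-week gap after Week 30, or earlier if a sample was missed.

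Finally, the share of late converters may be small. Early termination removes some late draws, as does the lack of ADA assessment at visits after an early end-of-treatment visit. This objection stands as a limit on size; it does not supply the missing cut-off.

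**Conclusion.** The point holds for the treatment-emergent split. As written, participants first detected positive at Week 56 or EOS are grouped as positive for a Week 30 HbA1c value, and the grouping varies with length of follow-up. This rests on reading treatment-emergent status by the only participant-level rule the SAP gives, the any-time rule in Section 2.4.5.7.

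The number of participants affected cannot be derived from the documents. The attenuation factor (1 − f) is illustrative and requires late converters to resemble ADA-negatives at Week 30; if they do not, the distortion could differ in size or direction.

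A reader might go on to doubt the primary result. There is no basis for that. Immunogenicity is a tertiary/exploratory objective, the table is descriptive and confined to the efpeglenatide arms, no test or alpha is attached, and non-inferiority does not depend on it. Nor would a correct cut-off make the comparison causal, since ADA status arises after randomisation. The change is worth making because the table would otherwise mix earlier and later antibody status and leave out the trial's primary time point.

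**What to change.** In the ADA paragraph of SAP 2.4.4.1:
- Summarise the HbA1c change from baseline to Week 56 by treatment-emergent ADA status, using only samples up to and including the Week 56 visit. This matches the time point of every other subgroup in that section.
- If the Week 30 table is kept, classify participants only on samples up to and including the Week 30 visit. Those first positive afterwards could be shown on a separate line.
- Report n in every cell.

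The cost is a few words of SAP text and one or two descriptive tables from data already being collected. The drawback is that the Week 56 table will hold fewer participants because of the early termination, which the reported n will make plain.
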